Upon consent, participants will be randomly assigned to Group #1 or Group #2. The study design is akin to a waitlist control design, with group #1 (treatment group) receiving 8 weeks of intervention followed by 8 weeks of continued use of TLC intervention tools, and group #2 (waitlist group) doing respite as usual for 8 weeks, followed by 8 weeks of more intensive coaching from the TLC intervention. Both group #1 and #2 will fill out daily/weekly reviews of their respite use throughout the calendar functions of the TLC intervention tools during the 16-week intervention period, as well as monthly questionnaires at baseline/enrollment, week 4, week 8, week 12, week 16, and week 20.

Note: when we created the online, self-administered version of the TLC intervention, we merged all data collection instruments with intervention prompts into a single online delivery package, so both group #1 and group #2 receive access to the TLC study tools from day 1 and end their access at the end of week 20. This has altered the traditional "waitlist" (i.e., no contact) condition associated with group #2. Both group #1 and group #2 receive the same instructions and orientation to the study on day 1. The groups differ only in the amount and type of "virtual coaching" (instructions and prompts from the TLC website) they receive at week 1 and week 9. Group #1 receives more intensive coaching at week 1, with an encouragement to continue doing it on their own at week 9. Group #2 receives less intensive coaching at week 1, with a more intensive coaching instructions presented to them at week 9.

Self-administered questionnaires and daily ecological momentary assessments (EMAs). Participants in both conditions will complete self-administered questionnaires at baseline, and then every 4 weeks thereafter (for a total of 6 questionnaires, spread across 20 weeks). All questionnaires will be distributed electronically via email. Responses will automatically be recorded in a secure REDCap data base.

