where Y_{ij} is the outcome measure (Caregiver Burden and Anxiety) for participant (i) at time (j) where j is an indicator for time (baseline, 4 weeks, 8 weeks, 12 weeks, 16 weeks and 20 weeks). β_0 is the population mean level of the outcome measure prior to the TLC intervention, β_1 fixed effect for time independent of intervention, X_{ij} is the intervention status (pre-TLC or Post-TLC/Follow-up) at timepoint j, and β_2 is the intervention treatment effect. Random effects include individual-level intercept (ζ_{0i}), individual-level slope of change over time ($\zeta_{1i} T_{ij}$), and ϵ_{ij} for residual error of each outcome measure. Our hypotheses for Aim 2 are summarized here:

Over time, we expect intervention engagement to produce more positive wellbeing, with time satisfaction as the mechanism through which TLC achieves its effect.

- H1:** Burden & anxiety will be lower among the treatment group compared to those in control/waitlist condition (direct effect)
- H2:** Time-use satisfaction will be higher among the treatment group compared to those in control/waitlist (direct effect)
- H3:** Higher time-use satisfaction will be associated with lower burden & anxiety (direct effect)
- H4:** Higher time-use satisfaction will mediate the effect of the intervention on burden and anxiety (direct & indirect effect)

H1: Burden & anxiety will be lower among the treatment group compared to those in control/waitlist condition (direct effect)

Figure 2: Anticipated results for Wellbeing with TLC

Our primary outcome will test the hypothesis that there will be significant change in “caregiver burden” or “anxiety” immediately post intervention. Figure 2 shows the anticipated results with no change during the run-in period, increase in wellbeing in Group A during the intervention but not WLC. Group B then shows increased wellbeing during TLC, with Group A maintaining or slight decrease in “caregiver burden” or “anxiety” over time. With the planned 120 participants (60 per group), we will be able to detect small to medium effect sizes on the two outcomes with greater than 90% Power (see below). Intent-to-treat analyses (ITT) will be performed on non-completers using a terminal score for both “caregiver burden” and “anxiety” scores.

H2: Time-use satisfaction will be higher among the treatment group compared to those in control/waitlist (direct effect)

[figure not shown]

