We assume clinically relevant small to medium effect sizes in the main outcomes of interest corresponding to 4-6.5 mean change on the total "caregiver burden" outcome and 1.0-1.4 mean change on the "anxiety" outcome. Power and sensitivity analysis were computed in GPower using RMANOVA finding a total sample of 116 would be sufficient to achieve

power of greater than 90% to detect these effect sizes. Therefore, we will aim to have a final sample size of 120 (60 in each sequence) with a 25% over-recruitment to account for study attrition providing a total sample size of 150.

Sample size and sensitivity analyses for mediation analyses are based on empirical estimates conducted by Fritz and MacKinnon (2007).¹²¹ Assuming medium effects for each of the two parts of the indirect pathways (i.e. TLC->Time-use and Time-use->Wellbeing) in Figure 3, a sample size of 75-120 will provide greater than 80% Power (Sobel148 medium-medium effects) at $p=0.05$.

Missing Data

We will explore missing data patterns in SPSS using the Missing Value Analysis tool. We will specify the pattern fixed effects and interactions utilizing Little's test for Missing Completely at Random. In keeping with an intent-to-treat standard and assuming maximum likelihood estimation, we will use all available data for analyses. It is not necessary to eliminate observations from participants who subsequently drop out, nor is it necessary to impute individual observations. Both practices can bias estimation and distort variability. The maximum likelihood estimates given the observed data points are the values most likely to have generated the complete ensemble of observed sample data under the assumed model. Systematic missingness (as determined by missing data patterns) may be included in our mixed effects model. Potentially non-ignorable missing data will be investigated using multiple imputation sensitivity analyses under a diverse set of covariate predictors. To minimize loss of scale scores due to missing items in a computed scale, we will prorate the respondent's score based on available items. If a respondent is missing more than 30% of the items in a computed score for the primary outcome variables, we will code the scale score as missing.

Note: feasibility is another primary outcome of the pilot test. Feasibility-related analyses are discussed at the end of this document, since the focus on feasibility and the analytic strategies to measure feasibility are shared across Aims 1, 2, and 3.

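### The >90% power claim is not re-justified for a control group that has the TLC tools from day 1, and it cannot be reproduced from the stated inputs

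*Combined protocol and SAP*

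**What the plan says.** **Power.** Under H1, the plan states that with 120 participants "we will be able to detect small to medium effect sizes on the two outcomes with greater than 90% Power". Power and Sample Size defines those effects in raw points only: "We assume clinically relevant small to medium effect sizes in the main outcomes of interest corresponding to 4-6.5 mean change" for burden, and "1.0-1.4 mean change on the" anxiety scale. On method it says: "Power and sensitivity analysis were computed in GPower using RMANOVA finding a total sample of 116 would be sufficient to achieve". The target named there is "power of greater than 90% to detect these effect sizes". The planned final sample is therefore 120, raised to 150 for attrition.

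**Contrast.** In Procedures, the paragraph on random assignment has group #2 "doing respite as usual for 8 weeks" before its intensive coaching. The note that follows says that data collection and intervention were merged into one online package, that both groups have access from day 1, and that this changed the usual waitlist condition. It adds: "The groups differ only in the amount and type of" virtual coaching, at weeks 1 and 9.

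The statistical section does not take this up. Study Design has a waitlist control. H1 compares treatment with control/waitlist. Equation 1 codes X as pre-TLC or post-TLC/follow-up, and the exploratory analyses describe X as TLC versus WLC.

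**The concern.** The randomised comparison described in Procedures is between two intensities of coaching among people who all use the same calendar and tools. The comparison that is powered and tested in the statistical section is TLC against a waitlist. Coding group B as pre-TLC while it already uses the tools would attach the label of TLC versus no TLC to an effect of coaching intensity.

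An effect of more versus less coaching may well be smaller than one of TLC versus nothing, so the power needs its own justification. The plan calls the sample fully powered. A null result could then be read as strong evidence against TLC, although the trial had not compared TLC with its absence and the power for the actual contrast was never stated.

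Separately, the power figure lacks the inputs needed to check it, and the text does not show which end of the effect range the 116 refers to.

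**Working it through.** **1. The two descriptions side by side**

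| | Procedures (note on random assignment) | Statistical section |
|---|---|---|
| Control group's access to tools | From day 1 | Waitlist; pre-TLC until TLC starts |
| Difference between groups | Amount and type of coaching | TLC versus WLC |
| Start of the contrast | Week 1 | After a 4-week orientation/control period |
| Control group's change-over | Week 9 | Week 12 |
| Effect assumed for this contrast | None given | Burden 4-6.5, anxiety 1.0-1.4 |

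**2. Attempt to reproduce 116**

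The inputs given are the raw effects, the method (GPower RM-ANOVA), N = 116 and power above 90%. Not given are the SD, the correlation ρ, the number of measurements m, the standardised effect f, the type of effect (between, within or interaction) and the alpha of the primary test. I assumed alpha 0.05, two groups and sphericity.

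- Between-groups effect: λ = f²Nm / (1 + (m−1)ρ), with df 1 and N−2.
- Interaction: λ = f²Nm / (1−ρ), with df m−1 and (N−2)(m−1).

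Three different settings have 116 as the smallest even total that reaches 90%:

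| Effect | f | m | ρ | λ | Power |
|---|---|---|---|---|---|
| Between | 0.25 | 3 | 0.5 | 0.0625×116×3/2 = 10.9 | 90.5% |
| Between | 0.25 | 6 | 0.6 | 0.0625×116×6/4 = 10.9 | 90.5% |
| Interaction | 0.125 | 4 | 0.5 | 0.015625×116×4/0.5 = 14.5 | 90.4% |

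The value of f differs twofold between these settings. The 116 therefore does not identify the assumptions behind it, and the claim can be neither confirmed nor refuted from the text.

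**3. Which end of the range?**

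At 90% power and two-sided 0.05, effect/SE = 1.960 + 1.2816 = 3.2415. Power for another effect in the range is Φ(3.2415 × ratio − 1.960).

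- If 116 was computed at the upper end, the ratio for burden is 4/6.5 = 0.615, and Φ(1.995 − 1.960) gives about 51%. For anxiety it is 1.0/1.4 = 0.714, and Φ(2.315 − 1.960) gives about 64%.
- If 116 was computed at the lower end, power at the upper end exceeds 99% for both outcomes, and the claim is true for TLC against waitlist.

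**4. What equation 1 can detect**

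Inputs from the plan are 60 per group, six assessments, and X switching on as in each of the two schedules above. Assumed are a common correlation ρ, no dropout and time either linear or categorical. The SE of β₂ is the generalised least squares SE in SD units, and the detectable difference is d = 3.2415 × SE.

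| ρ | Detectable d at 90% (range over both schedules and both codings of time) |
|---|---|
| 0.5 | 0.30-0.35 |
| 0.6 | 0.27-0.32 |
| 0.7 | 0.23-0.28 |
| 0.8 | 0.19-0.23 |

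For example, at ρ = 0.5 with categorical time, SE = 0.108 and d = 3.2415 × 0.108 = 0.35. At ρ = 0.8 with linear time and the Procedures schedule, SE = 0.0593 and d = 0.19. Adding the small random-slope variances that were tried moves the upper limit only from 0.350 to 0.353.

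**5. A smaller contrast (illustrative)**

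No passage says how much of the effect the shared tools already deliver. Suppose an effect is powered at exactly 90%:

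- attenuated by 25%: Φ(3.2415×0.75 − 1.960) = Φ(0.471), about 68%;
- attenuated by 50%: Φ(3.2415×0.50 − 1.960) = Φ(−0.339), about 37%.

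**The case against.** A reader might infer that the trial falls short of 90% power for small effects. The documents do not support that. They give raw points without an SD, so equating the lower end with d = 0.2 is an outside choice. It also fits the ranges poorly: their upper-to-lower ratios are 1.63 and 1.4, against 2.5 for d from 0.2 to 0.5. If the upper ends were d = 0.5 (an assumption), the lower ends would be 0.5 × 4/6.5 = 0.31 for burden and 0.5 × 1.0/1.4 = 0.36 for anxiety. Equation 1 would then reach 90% for anxiety throughout. It would also do so for burden except at the lower correlations, where power would still be about 81% or more. A detectable d of 0.19-0.35 is compatible with one reading of small to medium. This objection stands.

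A reader might also compute power for a single post-intervention visit and find it low. The plan specifies no such test: efficacy is tested with the multilevel model over all six assessments.

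Nor can one say that the power was left unrevised after the control condition changed. The power text is undated and its effect sizes name no comparator. One can say only that no justification for the smaller contrast appears.

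Finally, this is a Stage 1 pilot with feasibility as another primary outcome. The note discloses the altered control openly, and dosage analyses are planned. That lowers the stakes. It does not remove the conflict, because the plan itself claims a fully powered efficacy test against a waitlist.

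**Conclusion.** The point holds in two parts.

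- **Contrast.** This part rests on the text alone. Procedures reduces the group difference to coaching, while H1, X and the power claim remain those of TLC versus waitlist, with no effect size or power for the reduced contrast.
- **Power figure.** It cannot be reproduced, and it may not hold at the lower end: about 51% (burden) and 64% (anxiety) if 116 belongs to the upper end, but fully met for TLC against waitlist if it belongs to the lower end.

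Under equation 1 the trial detects d = 0.19-0.35 with 90% power. This assumes 60 per group, two-sided 0.05, correlation 0.5-0.8 and complete data. The loss from the smaller contrast is unknown; 68% and 37% illustrate 25% and 50% attenuation and are not estimates.

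**What to change.** 1. Reconcile the Procedures note with Study Design, H1 and the definition of X, including the differing start and change-over weeks, so that one description of the two groups applies throughout.
2. Word H1 and X as more intensive versus less intensive coaching with shared tools, and state that a null result does not speak to TLC versus no TLC.
3. Replace the claim of over 90% power for small to medium effects by the smallest difference detectable at 90% for the treatment coefficient of equation 1, for burden and for anxiety. Give the assumed SD, correlation, number of assessments and alpha, and say which end of each raw range it covers.
4. Add rows for an attenuated contrast, for example 25% and 50%, labelled as illustrative.

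No change to N is needed. The cost is rewording, a less favourable stated power and a narrower conclusion.

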Because this is part of early-stage intervention development activities (Stage 1), we have designed a clinical trial to pilot-test feasibility as well as efficacy of the redeveloped TLC intervention. We propose to use a waitlist control cohort design, using a fully powered sample to provide the most rigorous analysis possible. The waitlist design allows all participants to receive the intervention. As shown here in the figure, participants will be randomized to one of two sequences. After baseline data collection and an initial orientation/control period for the first 4 weeks, Group A will have 8 weeks of TLC intervention, then 8 weeks of follow-up. Group B will have 8 weeks of waitlist control, and then TLC intervention for 8 weeks, beginning at week 12. We will use ecological momentary assessment (EMA) during the entire 20-week study period to capture daily time-use trends for any respite periods received (n=140 daily reports, max). EMA aims to minimize recall bias and maximize ecological validity. Primary outcomes data will be collected via electronically administered surveys at baseline (T0) and every 4 weeks thereafter (T4, T8, T12, T16, T20), for a total of 6 assessments. This randomized, prospective, and longitudinal design

allows each participant to serve as its own control and offers opportunities to assess both within- and between-group differences over time (Group A vs. B).

Measures

The primary outcome is wellbeing, measured with two standardized scales indicating “caregiver burden” and “anxiety.” The mechanism driving the intervention effect is theorized to be related to respite time-use and time-use satisfaction. This construct is measured with “experienced” and “evaluative” time-use measures.

Analysis

The analysis to test for efficacy will specifically look at treatment x time interaction that combines both vertical (between individuals at given timepoints) as well as horizontal (evolution within individual over time) comparisons. We will utilize a multilevel model that consists of level 1 (within person) and level 2 (between person). Thus, the overall composite two level Multi-Level Mixed effects Model (MLM) is defined as follows with the first set of brackets representing fixed effects and second set random effects:

$$Y_{ij} = [\beta_0 + \beta_1 T_j + \beta_2 X_{ij}] + [\zeta_{0i} + \zeta_{1i} T_{ij} + \epsilon_{ij}] \quad [\text{equation 1}]$$

[figure not shown]

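### The H1 intent-to-treat rule rests on an undefined terminal score that is never ranked against the plan's likelihood rule and, if it means carry-forward, contradicts it

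*Combined protocol and SAP*

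**What the plan says.** Two places address intent-to-treat for the primary outcomes.

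- **H1, in the Analysis part of the statistical section:** "Intent-to-treat analyses (ITT) will be performed on non-completers using a terminal score for both" burden and anxiety scores. This is the only use of the term. The plan does not say which score is meant, which visits it applies to, or whether the analysis is primary or supplementary.
- **Missing Data:** "In keeping with an intent-to-treat standard and assuming maximum likelihood estimation, we will use all available data for analyses". The section adds that imputing individual observations is unnecessary and can bias estimates and distort variability. The only missing-data analysis it labels as sensitivity is multiple imputation.

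The efficacy model is equation 1, a two-level mixed model for burden and anxiety at T0, T4, T8, T12, T16 and T20: "The analysis to test for efficacy will specifically look at treatment x time interaction". Its treatment term X_ij "is the intervention status (pre-TLC or Post-TLC/Follow-up) at timepoint j".

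The timing of TLC is described in two ways. Under Study Design, after a 4-week orientation period, "Group A will have 8 weeks of TLC intervention, then 8 weeks of follow-up". Under Procedures, Group #1 starts at week 1, "receiving 8 weeks of intervention followed by 8 weeks of continued use of TLC intervention tools". Both schedules are used below because the illustration depends on which visits count as treated.

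**The concern.** Both rules claim the intent-to-treat label for the same two outcomes. If the terminal score is a value placed at visits where no survey was completed, it is imputation of individual observations, which Missing Data advises against. Two analysts following the plan could then report different ITT estimates for burden and anxiety, and the choice could be made after the data are seen.

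On the carry-forward reading the rule is also incomplete. Equation 1 needs a value of X_ij at every filled visit, and the plan does not give one. The analyst could use the scheduled status at that visit or freeze the status at the last completed survey. This is part of the same gap, because it arises once visits are filled in.

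**Working it through.** **1. Attrition (Power and Sample Size).** The plan recruits "with a 25% over-recruitment to account for study attrition providing a total sample size of 150". Check: 120 × 1.25 = 150, and 120/150 = 80%, so the allowance covers 20% loss. That is the dropout rate used below.

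**2. Time drift (H1).** "Figure 2 shows the anticipated results with no change during the run-in period", and no gain in the waitlist group. The base case therefore has no drift.

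**3. Assumptions not in the documents.** SD 1; between-visit correlation 0.6; random-slope SD 0.4 over 20 weeks; true effect -0.30 SD; TLC visits coded as treated; dropout random and even, so that in each group 80% complete and 4% have their last survey at each of T0, T4, T8, T12 and T16.

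**4. Visits coded as treated.**

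| Schedule | First group | Second group |
|---|---|---|
| Study Design | T8-T20 | T16-T20 |
| Procedures | T4-T20 | T12-T20 |

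**5. Method.** Equation 1 is Y_ij = β0 + β1·T_j + β2·X_ij + ζ0i + ζ1i·T_ij + ε_ij. Carry-forward replaces Y_ij after the last survey L by Y_iL. For each group and dropout pattern p, with share w_p, take the exact mean m_p and covariance of the observed or filled scores, with design matrix D_p and model covariance S_p. The large-sample estimate is β = (Σ w_p D_p' S_p⁻¹ D_p)⁻¹ Σ w_p D_p' S_p⁻¹ m_p, with the covariance parameters refitted by maximum likelihood. There is no Monte Carlo error.

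**6. Results, scheduled X_ij, no drift.**

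| Schedule | Likelihood | Carry-forward | Attenuation |
|---|---|---|---|
| Study Design | -0.300 | -0.265 | 0.035/0.300 = 12% |
| Procedures | -0.300 | -0.275 | 0.025/0.300 = 8% |

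Applied to the plan's own effect sizes, this is about 0.3 points (8% of 4) to 0.8 points (12% of 6.5) on burden, and 0.08 (8% of 1.0) to 0.17 (12% of 1.4) on anxiety.

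**7. Why it shrinks.** Some filled visits carry a pre-TLC score but are labelled treated. Count one cell for each dropout pattern and filled visit: each group has 5 + 4 + 3 + 2 + 1 = 15, or 30 in all. On the Study Design schedule, last surveys at T0 or T4 in Group A each give 4 such cells (8), and T0, T4, T8 or T12 in Group B each give 2 (8), so 16 of 30. On the Procedures schedule it is 5 in Group #1 and 3 × 3 = 9 in Group #2, so 14 of 30. These are cells, not participants.

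**8. Sensitivity.** Correlations of 0.4 or 0.8, or no random slope, leave the no-drift results almost unchanged (-0.264 to -0.266, and -0.274 to -0.277). If only post-TLC visits count as treated, carry-forward gives -0.254 (Study Design) and -0.265 (Procedures), which is 15% and 12%.

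**9. Power.** Equation 1 simulations on the Study Design schedule (75 per group, 20% even dropout, 1,000 replicates each) gave carry-forward against likelihood 94.5% v 94.2%, 96.6% v 97.0% and 94.8% v 94.9%. Power was not run for the Procedures schedule. A single-visit T12 contrast is a different analysis with different assumptions: effect -0.50 SD, half of it present at T8, last survey evenly at T0, T4 or T8, 75 per group. At 20% dropout it gave -0.42 against -0.50, with power about 72% against 83%.

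**The case against.** **The conflict is conditional.** If terminal score means an exit score actually obtained from people who leave, it is observed data and can enter the likelihood model. This stands. No exit survey is described, so carry-forward is the more natural reading, but the plan does not state either. What is certain is that the term is undefined and unranked.

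**The plan already points to likelihood.** Equation 1 is defined for burden and anxiety, Missing Data speaks of analyses in general, and the H1 sentence is confined to non-completers, which suits a supplementary analysis. This stands as a lean, and it limits the severity. It does not settle the matter, because Missing Data neither cites nor withdraws the H1 sentence, and that sentence is the one in H1 that names ITT.

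**A reader might infer that the rule inflates false positives.** The documents do not support that. With X_ij frozen at the last observed status, no true effect and a drift of 0.10 SD per visit, simulated rejection was 16.1% (Study Design) and 13.0% (Procedures). Frozen coding fits poorly with a status defined at each timepoint and with intent-to-treat. The drift amounts to 5 × 0.10 = 0.5 SD over the study, where the plan anticipates none before TLC. Without drift, frozen coding gives -0.300, unbiased. With drift of +0.10 or -0.10 it moves either way, to -0.242 or -0.358 on the Study Design schedule and -0.253 or -0.347 on the Procedures schedule. It is a secondary, less likely reading. With scheduled X_ij at drift 0.10, rejection was 4.7% and 4.2%, against 4.5% and 4.0% by likelihood.

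**A reader might also infer that power is unaffected, or that it is seriously harmed.** Neither holds in general. It depends on whether H1 is tested through equation 1's pooled coefficient or at one visit, and H1 is worded as change immediately after the intervention.

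**Conclusion.** The point holds as a wording fault with a conditional statistical consequence. It is high confidence that the terminal score is undefined, carries no sensitivity label and is not ranked against the likelihood rule. It is probable, not certain, that the two rules conflict, since that requires the terminal score to fill unobserved visits.

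On the carry-forward reading with scheduled X_ij, no drift and TLC visits coded as treated, the estimate is attenuated by 8-12% at the plan's own 20% attrition. The size rests on the assumed covariance, the coding of X_ij and the random, even dropout. Random dropout also makes likelihood unbiased by construction in these calculations; dropout that depends on the scores was not examined. The sample-size figures are not affected. This should be fixed, but it does not invalidate the design.

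**What to change.** In H1, state that the ITT analysis is the equation 1 mixed model, fitted by likelihood to all randomised caregivers using every observed survey. Then either delete the terminal-score sentence, or keep it with a definition (which score, which visits, X_ij at its scheduled status) and label it a sensitivity analysis.

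The cost is one sentence of wording and no new data. Deleting the sentence does drop that analysis. The multiple imputation sensitivity analysis in Missing Data remains, but the documents do not show that it answers the same question, so the team should decide whether it wants the terminal-score analysis before removing it.
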